Respiratory Biofeedback Sensor for Yoga Practice for Youth with Chronic Pain

NCT number: 05791435

1/3/22

Data Analysis:

Numeric data will be summarized using mean (SD) or median (Interquartile range) as appropriate, and categorical data will be summarized using frequencies and percentages. Baseline and demographic characteristics will be compared using t-test, Mann-Whitney U test or Fisher exact tests as appropriate. A mixed effects repeated measures analysis of variance (ANOVA) will be used to compare the mean changes in breathing phase angle (degrees), labored breathing index (unit), blood oxygen level (%), respiratory rate (unit), pain acceptance scale, PROMIS pediatric pain interference scale, and PROMIS youth anxiety short form over time. Likert scale measures will be used as both numeric and categorical forms, thereby, a generalized mixed effects model will also be used to compare the changes in Likert scale over time. Model assumptions will be checked before analysis. All tests will be two-tailed at the level of significance of 0.05. Statistical software SAS, version 9.4, or R (version 4.05) will be used for the analysis.

Sample size and power:

The primary goal is the change in breathing phase angle from baseline to after the yoga therapy regimen. In accordance with data from a previous study [29] the baseline mean (SD) phase angle is 40 (12) degrees, and after 8 weeks of yoga therapy we expect the phase angle to be 15 (9) and 30 (9) in the instructional + biofeedback group, and instructional alone group, respectively. A sample size of 8 subjects in each group can detect the above changes in phase angle with a power more than 80% at the level of the significance of 0.05. Assuming 25% attrition rate a sample size of 20 (10 + 10) subjects is planned for this study.

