- The *Chronic Pain Acceptance Questionnaire, Adolescent Version (CPAQ-A)* [31] is a 20-item self-report measure for youth with two subscales: 1) Pain Willingness (i.e., willingness to experience pain without attempting to control, reduce, or avoid it) and 2) Activity Engagement (i.e., participation in valued life activities despite pain). Questions are rated on a 5-point Likert scale from 0 (never true) to 4 (always true). Higher scores indicate greater pain acceptance. Prior research suggests the CPAQ-A has adequate psychometric properties [31,32,33].
- The *PROMIS Pediatric Pain Interference Scale* [34] is an 8-item self-report questionnaire assessing the extent to which pain interferes with functioning (e.g., emotional, academic, physical) over the past 7 days.

Items are rated from 1 (never) to 5 (almost always). Normative data are available, and raw scores are transformed to T-scores. Higher scores indicate greater levels of pain interference.

- The PROMIS Youth Anxiety Short Form [35] is an 8-item form derived from the item bank for Pediatric Anxiety developed by the NIMH-sponsored PROMIS. This measure assesses fear (e.g., fearfulness), anxious misery (e.g., worry), and hyperarousal (e.g., nervousness) over the past week. Adolescents and parents/guardians rate how often they experienced feelings in a variety of contexts, including home, school, and social activities on a scale from 0 (*never*) to 4 (*always*). Normative data are available, and raw scores are transformed to T-scores. Higher scores indicate greater levels of anxiety.

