Success of this feasibility study will be measured by statistically significant improvement in the standardized measures of pain before and after the yoga therapy regimen as a whole. Improvement in respiratory measures will be recorded after each session and as a cumulative measure. Longer term retention of gains made will not be measured due to time constraints but will be implemented in phase II.

Timeline

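### Likert measures are to be tested in both numeric and categorical form with neither named as deciding, which opens a second route to the study's success criterion

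*SAP*

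**What the plan says.** The SAP (Data Analysis) and the Protocol (Data analysis) use the same text. The mixed-effects repeated measures ANOVA covers, among other outcomes, the "pain acceptance scale, PROMIS pediatric pain interference scale, and PROMIS youth anxiety short form over time". The next sentence adds a second analysis: "Likert scale measures will be used as both numeric and categorical forms, thereby, a generalized mixed effects model will also be used". On error control, the only statement is "All tests will be two-tailed at the level of significance of 0.05".

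The Protocol's section on potential problems and benchmarks then gives these scales a deciding role: "Success of this feasibility study will be measured by statistically significant improvement in the standardized measures of pain", measured before and after the regimen.

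Under Pain Measures, the Protocol uses the word Likert for one instrument only, the CPAQ-A. Both PROMIS forms are reduced to a numeric score: "Normative data are available, and raw scores are transformed to T-scores". No categories or cut-points are given for any total or T-score.

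**The concern.** Two planned analyses address the same question on the same data, each at 0.05, and the text ranks neither above the other. It also leaves open which instruments are meant, whether the categorical outcome is an item or a total, how many categories there are, which link is used, and what happens if the two analyses disagree.

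For an exploratory outcome this would be a matter of tidiness. Here, statistical significance on the pain measures is the stated benchmark for success. As written, a significant result from either form could be reported as meeting it. Two analysts following the plan faithfully could reach opposite conclusions, and the undefined categories could be chosen after the data are seen.

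**Working it through.** **1. The plan's own figure.** The documents give no power or error rate for the questionnaires. The only calculation is for phase angle: post-regimen means 15 and 30, SD 9, 8 per group. The standardised difference is 15 / (9 × √(2/8)) = 15 / 4.5 = 3.33, and Φ(3.33 − 1.96) gives power of 91.5% (87.2% by noncentral t). The claim of more than 80% therefore reproduces on the post-regimen SD. Phase angle is not a Likert measure and is not analysed twice.

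**2. Data available.** The pain scales are measured twice. With 16 evaluable subjects there are 16 × 2 = 32 observations; with all 20 there are 40. A five-level outcome over 2 arms and 2 times has 5 × 2 × 2 = 20 cells, so 32/20 = 1.6 to 40/20 = 2 observations per cell. A five-category random-intercept cumulative-logit model with group, time and their interaction has 4 thresholds + 3 fixed effects + 1 variance = 8 parameters.

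**3. Benchmark for two tests.** If both tests had exact size 0.05 and were independent, the chance that at least one is falsely significant would be 1 − 0.95² = 0.0975. The two forms share data, so the excess is smaller than this if both hold their size, and larger if the categorical test does not.

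**4. Simulation with a fitted ordinal model.** There were 1,500 null trials per setting. Assumptions, none from the documents: a normal score, pre-post correlation 0.5, and a score cut into 2, 3 or 5 equally likely categories or 5 skewed ones. The numeric form was a t-test on change, standing in for the ANOVA. The categorical form was a random-intercept cumulative-logit model with a likelihood-ratio test. False-positive rates for change over time, either direction:

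| n | Categories | Numeric | Categorical | Either |
|---|---|---|---|---|
| 16 | 2 | 0.057 | 0.088 | 0.119 |
| 16 | 3 | 0.049 | 0.069 | 0.093 |
| 16 | 5 | 0.043 | 0.062 | 0.077 |
| 16 | 5, skewed | 0.060 | 0.082 | 0.107 |
| 20 | 2 | 0.061 | 0.087 | 0.123 |
| 20 | 3 | 0.044 | 0.055 | 0.077 |
| 20 | 5 | 0.045 | 0.062 | 0.076 |
| 20 | 5, skewed | 0.051 | 0.065 | 0.086 |

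Monte Carlo error is about 0.01 or less. The first row shows the overlap: 0.057 + 0.088 − 0.119 = 0.026 of trials had both forms significant, against 0.057 × 0.088 = 0.005 under independence. The tests are clearly correlated. The either-form rate passes 0.0975 in some rows because the categorical test itself exceeds 0.05.

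For group-by-time at n = 16, the either-form rate was 0.105-0.129.

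**5. Stability of the categorical model.** Estimates were degenerate (a coefficient above 8 in absolute value on the logit scale, or a random-effect SD above 10) in 1-13% of fits for time, and in 4-27% for group-by-time at n = 16. With five categories, 93-100% of data sets had at least one empty arm-by-time-by-category cell.

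**6. Simpler check, with direction.** A separate run used 20,000 null data sets per setting, pre-post correlation 0.5-0.7, assumed cut-points, and a sign-type test in place of the categorical model. It gave about 5% for the numeric form and 7.0-7.5% if either form counts. Counting only results in the direction of improvement, the rates were 2.4-2.7% and 3.5-3.8%.

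**The case against.** The strongest reply has four parts.

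- **The study is small and exploratory.** The primary goal is phase angle, this is a phase I feasibility study, and attribution is deferred to a later controlled trial. This limits the consequence, but the Protocol still ties success to significance on the pain measures, so the rule for declaring it should be clear.
- **Success requires improvement, not any change.** This stands. On the simpler check, the either-form rate for one scale in the improvement direction stays below 5%. A reader might infer that the double analysis alone pushes a single scale's success claim past 5%; the direction-specific figures do not show that.
- **The term Likert may cover only the CPAQ-A.** This also stands. A reader might infer that all three questionnaires are tested twice and combine the rates across them. The documents do not say so, and even with one form each, three independent scales would give 1 − 0.95³ = 14.3%. That part comes from having several scales with no deciding scale named, which is a separate matter.
- **The second model may be meant as a sensitivity analysis.** That would be sensible, but the text does not say it. It says only that the model is used as well.

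**Conclusion.** The point holds as a lack of ranking between two planned analyses. For any scale analysed in both forms, the false-positive rate rises from about 5% to about 7-12% if either form may count. In the improvement direction only, it rises from about 2.5% to about 3.5-4% on the sign-type check. These figures rest on assumed categories, correlations and model form, since the documents define none of them. The inflation is real but modest. The phase-angle goal and its power calculation are untouched.

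Two stronger readings should be resisted. One is that 16-20 subjects cannot support a categorical model at all. The model is not specified, and a simple ordinal or binary version gave non-degenerate estimates in most simulated data sets, so fragile and somewhat anticonservative is as far as the evidence goes. The other is that the scales will be tested item by item, with a much larger error rate. The documents plan no item-level testing.

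**What to change.** In both the SAP (Data Analysis) and the Protocol (Data analysis), replace the sentence on the two forms with:

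*The numeric score (T-score for the two PROMIS forms, total score for the CPAQ-A) is the only form used for inference and for the success criterion in the Protocol's benchmarks section. Any categorical analysis is a sensitivity or descriptive analysis and cannot establish success.*

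Deleting the generalized mixed model is optional. If it is kept, state before analysis which instruments it covers, whether the outcome is an item or a total, the categories and the link. The sentence should not introduce a between-arm, baseline-adjusted comparison, because success is framed as before versus after the regimen. It does not settle which scale or scales must be significant; that needs its own decision.

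The cost is a short edit in two places, with no effect on enrolment or data collection. The small downside is that the ordinal analysis no longer carries inferential weight.

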Data analysis: Numeric data will be summarized using mean (SD) or median (Interquartile range) as appropriate, and categorical data will be summarized using frequencies and percentages. Baseline and demographic characteristics will be compared using t-test, Mann-Whitney U test or Fisher exact tests as appropriate. A mixed effects repeated measures analysis of variance (ANOVA) will be used to compare the mean changes in breathing phase angle (degrees), labored breathing index (unit), blood oxygen level (%), respiratory rate (unit), pain acceptance scale, PROMIS pediatric pain interference scale, and PROMIS youth anxiety short form over time. Likert scale measures will be used as both numeric and categorical forms, thereby, a generalized mixed effects model will also be used to compare the changes in Likert scale over time. Model assumptions will be checked before analysis. All tests will be two-tailed at the level of significance of 0.05. Statistical software SAS, version 9.4, or R (version 4.05) will be used for the analysis.

Sample size and power: The primary goal is the change in breathing phase angle from baseline to after the yoga therapy regimen. In accordance with data from a previous study [29], the baseline mean (SD) phase angle is 40 (12) degrees, and after 8 weeks of yoga therapy we expect the phase angle to be 15 (9) and 30 (9) in the instructional + biofeedback group, and instructional alone group, respectively. A sample size of 8 subjects in each group can detect the above changes in phase angle with a power more than 80% at the level of the significance of 0.05. Assuming 25% attrition rate a sample size of 20 (10+10) subjects is planned for this study.

Potential problems, alternate strategies, benchmarks for success

Yoga is one of a few other therapies (cognitive behavioral therapy, physical and occupational therapy, massage, and/or medications) participants in this study may simultaneously be receiving. This makes it difficult to determine whether the breathing with biofeedback is the cause of improvement. However, this will be further examined in phase II with a controlled trial with a larger sample size.

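### The power of more than 80% for change in phase angle is unsupported for the named analysis: it needs a baseline-to-end correlation of about 0.58 or higher, and the plan gives none

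*SAP*

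**What the plan says.** The protocol and the SAP carry essentially the same text under the headings on data analysis and on sample size and power.

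- Primary quantity: "The primary goal is the change in breathing phase angle from baseline to after the yoga therapy regimen".
- Analysis: "A mixed effects repeated measures analysis of variance (ANOVA) will be used to compare the mean changes in breathing phase angle (degrees") and the other outcomes over time. Baseline as a covariate is not mentioned.
- Planning values: "the baseline mean (SD) phase angle is 40 (12) degrees", and at the end "we expect the phase angle to be 15 (9) and 30 (9) in the instructional + biofeedback group, and instructional alone group, respectively". A previous study is cited as the source.
- Power: "A sample size of 8 subjects in each group can detect the above changes in phase angle with a power more than 80" per cent, at the 0.05 level.
- Sidedness: "All tests will be two-tailed at the level of significance of 0.05".
- Size: "Assuming 25% attrition rate a sample size of 20 (10 + 10) subjects is planned for this study".

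Neither document gives an SD of change, a correlation between baseline and end values, or the test to which the power figure belongs.

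**The concern.** The precision of a change score depends on how strongly a subject's baseline and end values are related. Two single-time SDs do not determine it. The plan claims power for a change but supplies only those two SDs, so a reader cannot confirm the figure for the quantity called primary.

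The printed inputs do give more than 80% directly for a different comparison, that of end values alone, which does not use the baseline. For change, the same inputs give anything from well below 80% to well above it, depending on a number that the plan leaves out. At stake is how the trial's sensitivity is understood. At rho between 0 and 0.5, the chance of missing the planned 15-degree difference would be 54% to 27%, where the stated power implies under 20%.

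**Working it through.** **Inputs** (SAP and protocol, Sample size and power): baseline 40 (SD 12) for both groups; end 15 (SD 9) with biofeedback and 30 (SD 9) with instruction alone; n = 8 per group; two-sided alpha 0.05. The expected changes are 40 − 15 = 25 and 40 − 30 = 10, so the difference in change is 15. The difference in end values, 30 − 15, is also 15. Rho is an assumption, taken as the same in both groups and shown over a range.

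**Method.** Two-sample t-test with 2n − 2 = 14 df. The noncentrality is 15 / (SD × √(2/n)), and √(2/8) = 0.5. Power comes from the noncentral t distribution.

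**1. The plan's figure.** On end values with SD 9, the noncentrality is 15 / (9 × 0.5) = 3.33 and power is 87%. More than 80% is therefore reproduced by a comparison of end values. That test would already reach 82% with 7 per group.

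**2. Unadjusted comparison of change.** SD of change = √(12² + 9² − 2 × rho × 12 × 9) = √(225 − 216 × rho). With two time points, this is the group-by-time test in a repeated-measures ANOVA that leaves the baseline means unconstrained.

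| rho (assumed) | SD of change | Noncentrality | Power, 8 per group |
|---|---|---|---|
| 0 | 15.0 | 2.00 | 46% |
| 0.3 | 12.7 | 2.37 | 60% |
| 0.5 | 10.8 | 2.77 | 73% |
| 0.583 | 9.95 | 3.01 | 80% |
| 0.6 | 9.77 | 3.07 | 81% |
| 2/3 | 9.0 | 3.33 | 87% |

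The number per group needed for 80% power is 17, 13 and 10 at rho of 0, 0.3 and 0.5. A normal approximation is kinder (52% at rho 0, 79% at rho 0.5, crossing 80% at about 0.51), but the t distribution is the right reference at 8 per group.

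**3. End values adjusted for baseline.** Residual SD = 9 × √(1 − rho²), with 13 df. At rho 0 the SD is 9.00, the noncentrality 3.33 and power 87%. At rho 0.5 the SD is 7.79, the noncentrality 3.85 and power 94%. These figures take the groups as balanced at baseline. I allowed for chance imbalance by simulating 100,000 trials at each rho (bivariate normal, 8 per group, the same means and SDs). Power was then about 84% at rho 0 and 93% at rho 0.5, still above 80%.

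**The case against.** The strongest reply is that no error has been shown. The stated power holds for end values, and it holds for change if rho is about 0.58 or higher. Nothing in the documents makes a rho of 0 to 0.5 more likely than 0.6. This stands: what is established is a missing input and an unnamed test.

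A reader might infer that the sponsor powered an end-value t-test by mistake. The documents do not support that. Such a test needs only 7 per group, whereas 8 is exactly the minimum for a change-score test at rho of about 0.58 to 0.65. The planned number fits an unreported correlation at least as well.

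It can also be said that the named analysis need not be an unadjusted change score. The protocol (Approach; Specific aim 2) describes recordings around individual sessions as well as around the whole regimen, so the model may use more than two time points. The groups are randomised with one planning baseline mean, and a model that uses this would behave much like step 3. This is fair, but the plan specifies neither a baseline adjustment nor which time points enter the model.

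A literal reading of the power sentence extends the 80% claim to the instruction-alone group's own 10-degree fall. A paired t-test with n = 8 gives 37% at rho 0 and 61% at rho 0.5, reaching 80% only near rho 0.70. That reading is strained, because the sentence follows directly on a two-group contrast. Read instead as an overall change over time (mean fall (25 + 10)/2 = 17.5 in 16 subjects), power is 99% even at rho 0. The wording is loose, but it does not show a failed claim.

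Finally, this is a feasibility study. The protocol (Potential problems, alternate strategies, benchmarks for success) defines success on the pain measures and leaves the question of cause to a later, larger trial. Nothing there says that a null phase-angle result would count against biofeedback. This lowers the stakes, but the plan still makes a formal power claim and sets N from it.

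**Conclusion.** The point holds in conditional form. For an unadjusted between-group comparison of change, the stated power requires rho of about 0.58 or higher. At rho of 0 to 0.5 the power is 46% to 73%, which is 34 to 7 points below 80%; between 0.5 and 0.58 it runs from 73% to 80%. The documents give no rho, so the claim is unsupported for the analysis named.

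Two stronger conclusions should not be drawn: that the trial is underpowered, and that the figure was computed on the wrong test. The first depends on an unknown rho and on the absence of baseline adjustment. The second concerns a calculation that the documents do not show.

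The result rests on the plan's means and SDs, 8 evaluable subjects per group, a common rho, approximate normality and two time points.

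**What to change.** Keep N = 20 and amend the sample size paragraph in both documents in one of two ways.

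- **(a) Adjust for baseline.** Specify the primary contrast as the between-group difference in end-of-regimen phase angle with baseline phase angle as a covariate, and say so in the data analysis section. With 8 per group, power is about 87% at rho 0 and 94% at rho 0.5 (about 84% and 93% allowing for chance baseline imbalance). The claim of more than 80% then holds without knowing rho.
- **(b) Keep the change comparison.** State the rho assumed and its basis, and make the power conditional. Suggested wording:

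> For the between-group difference in change in phase angle (25 versus 10 degrees; SD 12 at baseline and 9 at end of regimen; two-sided 0.05), 8 subjects per group give about 46%, 60%, 73% and 81% power at baseline-to-end correlations of 0, 0.3, 0.5 and 0.6.

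In either case, replace the phrase 'the above changes' with that single between-group contrast, so that the sentence cannot be read as a claim about either group's own change.

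The cost is a one-paragraph edit in each document, plus a line in the analysis section under (a). No subjects are added. Under (b) the stated power becomes conditional and, at lower correlations, less favourable. Option (a) is preferable because it removes the dependence on an unknown quantity.
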